10.3.3. Secondary Endpoint 3 – Time to Major Amputation

Descriptive statistics for time to major amputation (above the ankle) of treated leg, time to doubling of index ulcer total surface area from baseline in treated leg, de novo gangrene in treated leg, time to reopening of closed ulcer, time to index ulcer total surface area reduction from baseline by 50%, and time to ulcer healing will be presented by cohort.

10.3.4. Secondary Endpoint 4 – Wagner Grading Scale

Wagner Grading Scale (Section 16.3) will be summarized using descriptive statistics by cohort at Screening and on Study Days 1, 8, 15, and 29 and Months 3, 6, 9, 12, and 24.

10.3.5. Secondary Endpoint 5 – Rutherford Criteria

Rutherford Criteria (Section 16.4 of the study protocol) will be summarized using descriptive statistics by cohort at Screening and on Study Days 1, 8, 15, and 29 and Months 3, 6, 9, 12, and 24.

10.3.6. Secondary Endpoint 6 – Leg Rest Pain

Leg rest pain will be summarized using descriptive statistics by cohort at Screening, on Study Days 1 and 8 prior to administration of PDA-002 and on Study Days 15 and 29 and Months 3, 6, 9, 12, and 24. Leg rest pain score will be measured on the visual analogue scale (VAS) graded from 0 (pain free) to Grade 10 (maximum pain).

10.3.7. Secondary Endpoint 7 – Overall Survival

Overall survival at 24 months (time from PDA-002 administration to any cause of death) will be summarized using descriptive statistics by cohort. Subjects still alive will be censored at the date of last follow-up.

10.3.8. Secondary Endpoint 8 – Incidence of Hospitalization

The incidence of hospitalization (all cause) will be summarized using descriptive statistics (frequency of hospitalizations, as well as duration) by cohort.

10.4. Subgroup Analysis

Due to the small sample size of this study, subgroup analyses for the primary endpoint will not be performed.

10.5. Analyses of Exploratory Efficacy Endpoints

Serum samples and peripheral blood mononuclear cells (PBMC) may be collected at Screening and Study Days 1, 8, 15, and 29, and Months 3 and 6 for the development of potential new biomarkers predictive of efficacy as well as to characterize the DFU population. Specific goals include: contribution to evaluation of safety and efficacy, evidence for repair and regeneration activity, and identification of universal pharmacodynamic biomarkers for PDA-002. Analysis of biological fluids and PBMCs will include the examination of research biomarkers as well as vascular and standard inflammatory markers.

Exploratory endpoints will be analyzed by the sponsor and a will not be described in this SAP.

11. SAFETY ANALYSIS

All summaries of safety data will be based on the Safety population. Descriptive statistics will be provided for safety summaries; no inferential testing for statistical significance or calculation of confidence intervals will be performed.

Adverse events observed will be classified using the Medical dictionary for Regulatory activities (MedDRA –version 17.1) classification system. The severity of the toxicities will be graded according to the National Cancer Institute (NCI) Common Terminology Criteria for Adverse Events (CTCAE) v 4.03 whenever possible. The frequency of adverse events will be tabulated by MedDRA System Organ Class and Preferred Term. In the by-subject analysis, a subject having the same event more than once will be counted only once. Adverse events will be summarized by NCI CTCAE grade. Adverse events leading to discontinuation from treatment, events classified as NCI CTCAE Grade 3 or higher, study-drug-related events, and serious adverse events will be tabulated and listed separately. By-subject listings of all adverse events, serious adverse events, discontinuations due to AEs, and deaths will be provided.

11.1. Dose Limiting Toxicities

A DLT is defined as a Grade 2 toxicity not resolving within 14 days suspected to be related to the IP or any toxicity \geq Grade 3 suspected to be related to the IP. Imputation of missing data will be used to define a DLT as follows:

- If the grade is missing, the grade will be imputed as \geq Grade 3.
- If the relationship is missing, the relationship will be imputed as suspected.

The frequency of DLTs will be tabulated. A by-subject listing of all DLTs will be provided.

11.2. Adverse Events of Special Interest

No adverse events of special interest have been pre-specified for this study.

11.3. Clinical Laboratory Evaluations

The change from baseline in the following laboratory parameters will also be summarized descriptively over time, by cohort and visit:

- a. Serum chemistry, lipid profile, fatty acids, hematology, urinalysis and pregnancy
- b. Coagulation tests
 - Prothrombin time (PT), partial thromboplastin time (PTT), and thrombin activation time (TAT)
 - D-dimers
 - Fibrinogen
 - Tissue factor procoagulant activity (TF-PCA)
 - Platelets
- c. Immunologic/Inflammation Assessments
 - Anti-HLA antibodies
 - C-reactive protein
 - Quantitative assessment of serum immunoglobulins (IgA, IgM, and IgG)
 - Vascular endothelial growth factor (VEGF)
 - Cytokines: interleukin (IL)-1 β , tumor necrosis factor (TNF- α), IL-6, IL-8, IL-10, and transforming growth factor- β (TGF- β)
- d. Tryptase and Histamine
- e. Troponin I
- f. Hemoglobin A1c
- g. Circulating endothelial cells (CECs)

Spaghetti plots of individual lab values and change from baseline values over time will be provided for these lab parameters.

By-subject listings will also be provided for the laboratory data.

11.4. Vital Sign Measurements

Summary statistics (N, Mean, Standard Deviation, Median, Minimum, and Maximum) of observed and change from baseline values will be presented by cohort and visit for the following vital signs:

- Temperature (°C),
- Pulse (beat/minute),
- Respiration (breaths/minute)
- resting systolic blood pressure (mmHg)
- resting diastolic blood pressure (mmHg).

A by-subject listing of vital signs during IP administration will be provided, including heart rate, respiration, blood pressure, body temperature, and pulse oximetry. This listing will identify vital sign values higher or lower than the normal range (Appendix XX.X).

11.5. Physical Examination

Physical exam results will be summarized in frequency tables by body systems and cohort.

11.6. Electrocardiogram

The average of the triplicate values taken on the same day will be calculated for each quantitative measure. Summary statistics (n, mean, SD, median, and range) for observed values and changes from baseline will be provided by cohort and visit for QT, QTcB, QTcF, PR, RR, QRS intervals, ST deviation, QRS axis, and heart rate. Individual values and day means will be presented in the listing.

11.7. MRI/CT Scans

Results of MRI/CT scans of the chest, abdomen, and pelvis will be summarized by cohort and visit. Cross-tabulations presenting shifts from baseline category (normal and abnormal values) by cohort and visit will also be presented.

11.8. Retinal exam

Retinal exam data will be summarized by cohort and visit. Cross-tabulations presenting shifts from baseline category (normal and abnormal values) by cohort and visit will also be presented.

11.9. Injection Site Assessment

An injection-related reaction is defined as any sign or symptom experienced by a subject during the injections or any event occurring within 24 hours of the IP administration. Summaries of injection-related reactions will be presented by cohort, including the duration and severity of injection-related reactions.

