### 3. STUDY ENDPOINTS

#### 3.1. Primary Endpoints

The primary endpoint is determination of the MTD defined as the highest PDA-002 dose level for which the incidence of DLT is  $\leq 1$  out of 6 subjects. Safety will be assessed by the frequency and severity of adverse events. To this end, the following safety assessments will be performed.

1. AEs including DLTs and serious adverse events (SAEs).
2. Vital signs, height and weight, and physical examinations.
3. Laboratory tests.
  - a. Serum chemistry, lipid profile, fatty acids, hematology, urinalysis and pregnancy
  - b. Coagulation tests
    - Prothrombin time (PT), partial thromboplastin time (PTT), and thrombin activation time (TAT)
    - D-dimers
    - Fibrinogen
    - Tissue factor procoagulant activity (TF-PCA)
    - Platelets
  - c. Immunologic/Inflammation Assessments
    - Anti-HLA antibodies
    - C-reactive protein
    - Quantitative assessment of serum immunoglobulins (IgA, IgM, and IgG)
    - Vascular endothelial growth factor (VEGF)
    - Cytokines: interleukin (IL)-1 $\beta$ , tumor necrosis factor (TNF- $\alpha$ ), IL-6, IL-8, IL-10, and transforming growth factor- $\beta$  (TGF- $\beta$ )
  - d. Tryptase and Histamine
  - e. Troponin I
  - f. Hemoglobin A1c
  - g. Circulating endothelial cells (CECs)
  - h. Urinary Cotinine
4. Assessment of injection sites.
5. Electrocardiograms (ECGs).
6. Retinal examinations.
7. Magnetic resonance imaging (MRI) or computed tomography (CT) of the chest, abdomen, and pelvis.
8. Concomitant medications and procedures.

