## **6.2. Treatment**

Subjects will be treated with IP administered IM on Study Days 1 and 8. In the case of bilateral limb ulcers, the treated limb will be the limb that has the largest ulcer total surface area. Prior to dosing with the IP, subjects will undergo a physical examination, including weight and vital signs, an ECG, and a review of concomitant medications and procedures. Blood samples for serum chemistry, hematology, troponin I, lipids and fatty acid analysis, immunological/inflammation assessments, hemoglobin A1c (Study Day 1 only), tryptase, histamine, CECs, exploratory biomarkers, and coagulation assessments should be drawn on the day of treatment prior to dosing with the IP. A urinalysis, a urine pregnancy test in females of child bearing potential, and a urinary cotinine test should also be performed prior to dosing with IP. Assessment of Rutherford Criteria, Wagner Grading Scale for foot lesions, measurement/assessment and photographs of ulcers, and determination of ABI, TBI, and leg rest pain score (VAS), should be performed on Study Days 1 and 8.

Investigational product will be thawed and diluted as per the pharmacy manual. Thawing of the IP should not begin until it is confirmed that the subject meets all eligibility criteria. The injections of IP (PDA-002) will be administered as described in Section 8.2. Vital signs (including heart rate, respiration, resting systolic and diastolic blood pressure, body temperature, and pulse oximetry) will be monitored prior to starting the injections and every 15 minutes for a minimum of 2 hours after completion of the injections. Blood samples for tryptase and histamine, coagulation assessments, CECs, and exploratory biomarkers will be collected approximately 2 hours after the injections have been completed. The injections must be completed within 4 hours of IP thaw time. Injection sites will be assessed. See Section 6.4.4 regarding injection site reactions.

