## **6.4. Safety**

Safety will be assessed by an ongoing review of clinical laboratory tests (hematology, serum chemistry, lipids, fatty acids, coagulation, troponin I, pregnancy, urinalysis, immunological/inflammation), physical examination results, vital sign measurements, 12-lead electrocardiogram (ECG), evaluations by MRI or CT scans of the chest, abdomen and pelvis, retinal exams, use of concomitant medications/procedures, and the incidence and severity of injection site and injection-related reactions (including tryptase and histamine) and treatment-emergent AEs.

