#### **6.4.4. Injection-Related Reactions**

An injection-related reaction is any sign or symptom experienced by a subject during the injections or any event occurring within 24 hours of the IP administration. The duration and severity of injection-related reactions will be collected and recorded on the eCRF.

Any allergic reaction  $\geq$  Grade 3 and associated with the IP is to be reported as a SAE.

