### **10.7. Safety Analysis**

The Safety analyses will be conducted using the Safety Population as defined in Section 10.2. Adverse events, vital sign measurements, physical examination findings, clinical laboratory test results, injection site assessments, MRI/CT scan results, retinal examination results, ECG interpretations, concomitant medications and procedures will be tabulated and summarized by cohort, as appropriate.

Adverse events observed will be classified using the Medical dictionary for Regulatory activities (MedDRA) classification system. The severity of the toxicities will be graded according to the National Cancer Institute (NCI) Common Terminology Criteria for Adverse Events (CTCAE) v 4.03 whenever possible.

[http://ctep.cancer.gov/protocolDevelopment/electronic\\_applications/ctc.htm#ctc\\_40](http://ctep.cancer.gov/protocolDevelopment/electronic_applications/ctc.htm#ctc_40)

The frequency of adverse events will be tabulated by MedDRA System Organ Class and Preferred Term. In the by-subject analysis, a subject having the same event more than once will be counted only once. Adverse events will be summarized by NCI CTCAE grade. Adverse events leading to discontinuation from treatment, events classified as NCI CTCAE Grade 3 or higher, study-drug-related events, and serious adverse events will be tabulated and listed separately. By-subject listings of all adverse events, serious adverse events, discontinuations due to AEs, and deaths will be provided.

Clinical laboratory data will be summarized. Laboratory data will be graded according to NCI CTCAE version 4.03 criteria wherever possible. The frequencies of the worst severity grade observed during treatment will be displayed in cross-tabulations by screening status.

Vital signs, ECG, retinal examination and MRI/CT scan data will be summarized by cross-tabulations presenting normal and abnormal values.

Graphical displays will be provided where useful in the interpretation of results.

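### SAP 11.9, headed Injection Site Assessment, summarises only 24-hour injection-related reactions, so local reactions starting later are not grouped by dose and unrelated same-day events are counted

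*SAP*

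**What the plan says.** Protocol 3.1 gives "Assessment of injection sites" as safety item 4, and SAP 4.2.4 repeats it. Protocol 6.4 treats local and time-based reactions as two things: safety review is to cover "the incidence and severity of injection site and injection-related reactions". Protocol 10.7 includes site assessments among the data to be summarised by cohort: "clinical laboratory test results, injection site assessments, MRI/CT scan results".

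Protocol 6.2 says that injection sites will be assessed and then directs the reader: "See Section 6.4.4 regarding injection site reactions". Section 6.4.4, however, defines only injection-related reactions, meaning any sign or symptom during the injections or "any event occurring within 24 hours of the IP administration".

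SAP 11.9 carries the title Injection Site Assessment, repeats the 24-hour definition almost unchanged, and plans one analysis: "Summaries of injection-related reactions will be presented by cohort, including the duration and severity of injection-related reactions". SAP 14, which lists departures from the protocol's analysis section, does not mention injection sites.

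**The concern.** Safety of the intramuscular route is a primary objective. Protocol 4.2 describes this as the first trial of PDA-002 by that route, and Protocol 8.2 has 15 injections on each of two days. A reader of the study report will look for one table showing local tolerability by dose, and SAP 11.9 is where its heading says that table will be.

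The definition used there does not fit a local endpoint. It has no anatomical criterion, so an event anywhere in the body qualifies. It has no causality criterion, although Protocol 11.2.3 requires the investigator to record one. It also closes 24 hours after each dose, so induration or inflammation at an injected site that begins on the third day is outside it. With 3 to 6 subjects per cohort, moving one or two events in or out of this table can change how the doses appear to compare.

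**Working it through.** No figure in the plan needs reproducing, because the analysis is descriptive. The check is to apply SAP 11.9 as written to each kind of event.

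| Event | Counted in SAP 11.9? | Belongs in a local summary? |
|---|---|---|
| At an injected site, onset within 24 h, seen the same day | Yes | Yes |
| At an injected site, onset within 24 h, first examined at Day 8 or Day 15 | Yes, if the start date is recorded accordingly | Yes |
| At an injected site, onset after 24 h | No | Yes |
| Elsewhere in the body, not suspected, onset within 24 h (for example, a hypoglycaemic episode 20 hours after dosing) | Yes | No |
| Elsewhere in the body, suspected, onset within 24 h | Yes | No, but properly an injection-related reaction |

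The third and fourth rows are the errors.

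**Does another SAP section fill the gap?**
- SAP 11 tabulates all adverse events by system organ class, preferred term and grade, with related events shown separately and by-subject listings. It specifies no grouping by injection site and no onset relative to dose.
- SAP 11.1 tabulates dose-limiting toxicities with no 24-hour limit. A suspected local reaction of Grade 1, or of Grade 2 that resolves within 14 days, does not meet that definition.
- SAP 11.2 pre-specifies no events of special interest.
- SAP 11.5 tabulates physical examination results by body system, not by injected site.

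A delayed, low-grade local reaction is therefore reported but not grouped with others of its kind.

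**How is timing observed?** Protocol 6.2 and 8.2 require monitoring for at least 2 hours after the injections. The next scheduled evaluations are Day 8 and Day 15, each 7 days after a dose. For anything that develops after the subject leaves, placing its onset inside or outside the 24 hours depends on the reported start date (Protocol 11.2.4).

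**How often would unrelated events enter?** The documents give no rate. Let q be an assumed chance of an unrelated event in any one 24-hour window, with windows independent. Each subject contributes two windows (Days 1 and 8), so for n subjects P(at least one) = 1 − (1 − q)^(2n), and the expected number is 2nq.

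| Assumed q | n = 3 (6 windows) | n = 6 (12 windows) | n = 24 (48 windows) | Expected, n = 24 |
|---|---|---|---|---|
| 1% | 6% | 11% | 38% | 0.5 |
| 3% | 17% | 31% | 77% | 1.4 |
| 5% | 27% | 46% | 91% | 2.4 |
| 10% | 47% | 72% | 99% | 4.8 |

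For example, with q = 3% and n = 6: 1 − 0.97^12 = 0.31. This illustrates the inclusion error only. No comparable calculation is possible for the omission, because nothing in the documents gives the distribution of onset times.

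**The case against.** The strongest reply is that the SAP follows the protocol and that no safety information disappears. Most of this stands.

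- A reader might infer that the SAP replaced the endpoint and concealed the change. The documents do not support that. The item is still listed in SAP 4.2.4, the 24-hour wording comes from Protocol 6.4.4, and Protocol 6.2 already routes injection site reactions there. What is missing is an analysis of the listed item, and both documents contribute to that.
- A reader might infer that any local finding first seen at the next visit is excluded. It is not: the criterion is when the event occurred, not when it was detected. SAP 11.9 also reports duration, so a reaction that starts in the window is described beyond it.
- A reader might set two 24-hour windows against the 14-day escalation period and take the ratio as the proportion of reactions missed. That is a calendar ratio and says nothing about when reactions begin.
- A reader might infer that delayed reactions go unreported. Adverse events are collected to Month 24, examinations at every visit cover skin and extremities, and a clinically significant worsening is recorded as an adverse event (Protocol 6.4.5).
- Escalation rests on dose-limiting toxicities and committee review of all safety information, not on SAP 11.9. Counting everything near dosing is a defensible, cautious choice for an injection-related measure.

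Two limits on the evidence also apply. The Table of Events is redacted, so the days on which sites are inspected cannot be confirmed beyond the dosing days. The case report form is not available, so a field for event location cannot be assumed.

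None of this supplies the by-cohort site summary that Protocol 10.7 promises. A broad 24-hour measure is reasonable as an injection-related summary. It does not serve as the injection-site summary.

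**Conclusion.** The point holds as a gap in analysis and reporting. Followed exactly, SAP 11.9 gives a table under the injection-site heading that omits local reactions with onset after 24 hours and includes same-day events that are neither local nor suspected. No other section of the SAP groups local findings by dose. The conclusion rests on the wording of the two documents and needs no assumption about rates; the 11% to 72% for a six-subject cohort depends on the assumed q of 1% to 10%.

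The consequence is limited. Delayed reactions recorded as adverse events remain in the general tables and listings, and in the dose-limiting toxicity assessment if they qualify. What is lost is a direct view of local tolerability across doses. It should be corrected before the SAP is signed for the interim database lock.

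**What to change.** In SAP 11.9, present two separate by-cohort summaries:

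1. **Injection-site reactions.** Site-assessment findings and adverse events located at an injected site, whatever the onset time, with maximum grade, onset in days from the most recent dose, and duration. The sources are the site assessments, the adverse event terms and dates, and the skin and extremity examinations already done at every visit.
2. **Injection-related reactions.** The existing 24-hour measure, under its own heading, split by suspected and not suspected.

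Reconcile Protocol 6.2 and 6.4.4 so that injection-site reactions are not defined by the 24-hour window. If the sponsor decides not to summarise site assessments, SAP 14 should declare that as a departure from Protocol 10.7, and SAP 11.9 should be retitled.

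The cost is one more descriptive table, some SAP wording and a corrected cross-reference, with no added visits. If the case report form has no location field, location will have to be taken from the reported adverse event term, and the SAP should state the rule for doing so.

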12. INTERIM ANALYSIS

An interim analysis of efficacy and safety will be performed after the last subject in the study has completed Visit 5 (Month 3) and all relevant study data have been processed and integrated into the analysis database.

12.1. Statistical Approaches for Control of Alpha

Formal statistical testing and interpretation of the statistical significance of results from analyses will not be performed. For this reason, statistical approaches for control of alpha for interim analyses are not applicable to this study.

13. DATA MONITORING COMMITTEE

An internal DMC will monitor all safety information to ensure subject safety. The internal DMC will be comprised of members who are not involved in the day-to-day activities of the PDA-002 DFU study team. The internal DMC will recommend whether continued dosing is appropriate, whether dose-escalation can occur, whether modifications to the protocol design are necessary or whether to end dosing and/or further enrollment at either a specific dose level or for the overall study. The internal DMC will make determinations on study continuation and modifications based on available AE and clinical data. Statistical reporting and operational details for the DMC are described in a separate DMC charter.

